9.2.3. Serious Adverse Events

Serious Adverse Event (SAE): An adverse event or suspected adverse reaction is considered “serious” if, in the view of either the investigator or sponsor, it results in any of the following outcomes:

- Death,
- a life-threatening adverse event¹,
- inpatient hospitalization or prolongation of existing hospitalization,
- a persistent or significant incapacity or substantial disruption of the ability to conduct normal life functions, or
- a congenital anomaly/birth defect.
- Important medical events that may not result in death, be life-threatening, or require hospitalizations may be considered serious when, based upon appropriate medical judgment they may jeopardize the patient or subject and may require medical or surgical intervention to prevent one of the outcomes listed in this definition. Examples of such medical events include allergic bronchospasm requiring intensive treatment in an emergency room or at home, blood dyscrasias or convulsions that do not result in inpatient hospitalization, or the development of drug dependency or drug abuse.

¹ Life-threatening adverse event. An adverse event is considered “life-threatening” if, in the view of either the site principal investigator or sponsor, its occurrence places the patient or subject at immediate risk of death. It does not include an adverse event, had it occurred in a more severe form, might have caused death.

SAEs will be:

- Assessed for severity and relationship to study product and alternate etiology.
- Recorded on the appropriate SAE data collection form and eCRF.
- Followed through resolution.
- Reviewed and evaluated by an Independent Safety Monitor (ISM) (as deemed necessary), the SMC (periodic review unless related), DMID, and the IRB.

9.2.4. Procedures to be Followed in the Event of Abnormal Laboratory Test Values or Abnormal Clinical Findings

The site principal investigator or appropriate sub-investigator is responsible for recording all AE/SAEs/MAAEs that are observed or reported during this trial, regardless of the relationship to study product. AE/SAEs/MAAEs, abnormal laboratory test values, or abnormal clinical findings will be collected, assessed, documented, reported, and followed appropriately.

For baseline laboratory results that are abnormal according to the local laboratory reference range and fall within Grade 1 toxicity table range, these will not be considered laboratory adverse event (AE) and will thus not be graded. However, if baseline clinical labs fall within Grade 1 range, then a laboratory AE is reported only if the value changes such that it falls into Grade 2 or higher when subsequent safety laboratory testing is done.

9.3. Reporting Procedures

Solicited local and systemic AEs will be documented and reported from the time of study vaccination through 7 days after each study vaccination.

Clinical safety laboratory adverse events will be documented and reported on Days 1, 8, 15, 29 and 36. The clinical safety laboratory tests will be collected prior to vaccination on Days 1 and 8. Additional safety labs will be collected and AEs reported if the subject returns to the clinic for re-evaluation of laboratory adverse events until resolution.

Unsolicited non-serious AEs will be documented and reported from the time of study vaccination through approximately 28 days after the second study vaccination.

SAEs (including lab values that meet SAE criteria), MAAEs will be documented and reported from the time of study vaccination through approximately 6 months after the first study vaccination.

At any time after completion of this trial, if the site principal investigator or appropriate sub-investigator becomes aware of an SAE that is suspected to be related to study product, the site principal investigator or appropriate sub-investigator will report the event to the DMID Pharmacovigilance Group.

9.3.1. Serious Adverse Events

SAEs will be followed until resolution even if this extends beyond the study-reporting period. Resolution of an AE is defined as the return to pretreatment status or stabilization of the condition with the expectation that it will remain chronic.

Any AE that meets a protocol-defined serious criterion must be submitted immediately (within 24 hours of site awareness) on an SAE form to the DMID Pharmacovigilance Group, at the following address:

DMID Pharmacovigilance Group
Clinical Research Operations and Management Support (CROMS)
[name] [name] 650
[name], USA
SAE Hot Line: [name] (US) or [name] (outside US)
SAE [contact] (US) or [name] (outside US)
SAE Email Address: [contact]

In addition to the SAE form, select SAE data fields must also be entered into the DCC system (for example: Advantage EDC). Please see the protocol-specific MOP for details regarding this procedure.

Other supporting documentation of the event may be requested by the DMID Pharmacovigilance Group and should be provided as soon as possible.

The site will send a copy of the SAE report(s) to the ISM (as deemed necessary) when they are provided to the DMID Pharmacovigilance Group. The DMID Medical Monitor and DMID Clinical Project Manager will be notified of the SAE by the DMID Pharmacovigilance Group. The DMID Medical Monitor will review and assess the SAE for regulatory reporting and potential impact on study subject safety and protocol conduct.

At any time after completion of the study, if the site principal investigator or appropriate sub-investigator becomes aware of an SAE that is suspected to be related to study product, the site principal investigator or appropriate sub-investigator will report the event to the DMID Pharmacovigilance Group.

9.3.2. Regulatory Reporting for Studies Conducted Under DMID-Sponsored IND

Following notification from the investigator, DMID, the Investigational New Drug (IND) sponsor, will report any suspected adverse reaction that is both serious and unexpected. DMID will report an adverse event as a suspected adverse reaction only if there is evidence to suggest a causal relationship between the drug and the adverse event. DMID will notify FDA and all participating investigators (i.e., all investigators to whom the sponsor is providing drug under its IND(s) or under any principal investigator's IND(s)) in an IND safety report of potential serious risks from clinical trials or any other source, as soon as possible, but in no case later than 15 calendar days after the sponsor determines that the information qualifies for reporting as specified in 21 CFR Part 312.32. DMID will also notify FDA of any unexpected fatal or life-threatening suspected adverse reaction as soon as possible, but in no case later than 7 calendar days after the sponsor's initial receipt of the information. Relevant follow up information to an IND safety report will be submitted as soon as the information is available. Upon request from FDA, DMID will submit to FDA any additional data or information that the agency deems necessary, as soon as possible, but in no case later than 15 calendar days after receiving the request.

All serious events designated as "not related" to study product(s), will be reported to the FDA at least annually in a summary format.

9.3.3. Other Adverse Events

N/A

9.3.4. Reporting of Pregnancy

Pregnancies occurring in study subjects will be reported via AdvantageEDCSM on the Pregnancy Report form. With the subject's permission, all protocol-required venous blood samples will be obtained and the subject will continue to be followed for safety for the duration of this trial. Efforts will be made to follow all pregnancies reported during the course of this trial to pregnancy outcome pending the subject's permission.

9.4. Type and Duration of Follow-up of Subjects after Adverse Events

AEs will be collected, assessed, and followed through resolution from the time of study vaccination through approximately 28 days after the second study vaccination.

SAEs and MAAEs will be collected, assessed, and followed from the time of study vaccination through resolution even if this extends beyond the trial-reporting period (approximately 6 months after the first study vaccination).

Resolution of an AE/SAE/MAAE is defined as the return to pretreatment status or stabilization of the condition with the expectation that it will remain chronic.

Follow-up procedures, evaluations, and outcomes will be recorded on the appropriate data collection form.

9.5. Halting Rules

Further enrollment and study vaccinations will be halted for SMC review/recommendation if any of the following are reported:

- Any subject experiences a study product-related SAE from the time of the study product administration through the subject's last study visit.
- Any subject experiences laryngospasm, bronchospasm, or anaphylaxis within 1 day after administration of study product that is considered related to study product.
- Two or more subjects experience generalized urticaria (defined as occurring at more than two body parts) within 3 days after administration of study product that is considered related to study product.
- Two or more subjects experience the same grade 3 unsolicited AE (in the same MedDRA High Level Term) after administration of study product that is considered related to study product and not resolved or improved to lower grade within 2 days.
- Two or more subjects experience the same grade 3 laboratory adverse event that is considered related to study product.

This trial will also be halted for SMC review/recommendation if, within 7 days after administration of any study vaccination, any of the following occurs:

- Two or more subjects experience the same grade 3 solicited local adverse event that is considered related to study product and not resolved or decreased to lower grade within 2 days.
- Two or more subjects experience the same grade 3 solicited systemic adverse event that is considered related to study product and not resolved or decreased to lower grade within 2 days.

Grading scales for solicited local (application site) and systemic (subjective and quantitative) AEs are included in [Section 9.2.2](#).

Grading scales for clinical safety laboratory adverse events are included in [Section 9.2.2](#).

If any of the halting rules are met following any subject receipt of any study vaccination, then this trial will not continue with the remaining enrollments or study vaccinations without a review by and recommendation from the SMC to proceed.

DMID retains the authority to suspend additional enrollment and study interventions/administration of study product during the entire trial, as applicable.

9.6. Safety Oversight (ISM plus SMC)

9.6.1. Independent Safety Monitor (ISM)

An ISM is a physician with relevant expertise whose primary responsibility is to provide to DMID an independent safety assessment in a timely fashion. Participation is for the duration of the DMID study and is a voluntary position that does not receive payment. The ISM must meet the requirements of the NIAID conflict of interest policy.

The ISM:

- Is in close proximity to the study site and has the authority and ability to readily access study participant records in real time.
- May be a member of the participating institution's staff but preferably be from a different organizational group within the institution.
- Should not be in a direct supervisory relationship with the investigator.
- Should have no direct involvement in the conduct of the study.

The ISM will:

- Sign a Conflict of Interest (COI) certification at the time they are asked to participate and provide updates to this information as needed.
- Receive reports of Serious Adverse Events (SAEs) from the site investigator and will be notified by email when DMID is notified of the SAE.
- Evaluate the SAE and report their clinical assessment to DMID, through DMID-CROMS SOCS in a timely manner using the attached report form and email the report to DMID-CROMS SOCS.
- Communicate with the investigator at the participating site as needed.
- Review additional safety related events at the request of DMID.
- Provide additional information to DMID and/or the SMC by teleconference as requested.

9.6.2. Safety Monitoring Committee (SMC)

This clinical study will utilize an SMC, which is an independent group of experts that advises DMID. The primary responsibility of the SMC is to monitor subject safety. The SMC is external to the DMID and comprises at least 3 voting members. The SMC will consist of members with appropriate Phase 1 study expertise to contribute to the interpretation of the data from this trial. Its activities will be delineated in a SMC charter that will describe the membership, responsibilities, and the scope and frequency of data reviews. The SMC will operate on a conflict-free basis independently of the study team. The DMID or the SMC may convene ad hoc meetings of the SMC according to protocol criteria or if there are concerns that arise during the study.

The SMC will review the safety data at the following milestones:

- Organizational meeting (prior to start of the study)
- Scheduled Data Review meetings
- An SMC Ad Hoc meeting will be convened when a halting rule is met, or at the request of the investigator and/or DMID if there are safety concerns during the course of the study.
- Final review meeting, to be conducted 6 to 8 months after clinical database lock to review the cumulative unblinded safety data for the study. The data will be provided in a standard summary format. The SMC may be asked to provide recommendations in response to questions posed by the DMID.

The SMC will operate under the rules of a DMID-approved charter that will be written at the organizational meeting of the SMC. At this time, each data element that the SMC needs to assess

will be clearly defined. Procedures for SMC reviews/meetings will be defined in the charter. The SMC will review applicable data to include, but not limited to, study progress and participant, clinical, safety, and reactogenicity data. Reports may include enrollment and demographic information, medical history, concomitant medications, physical assessments, clinical laboratory values, dosing compliance, and solicited and unsolicited AE/SAEs/MAAEs. Additional data may be requested by the SMC, and interim statistical reports may be generated as deemed necessary and appropriate by DMID. The SMC may receive data in aggregate and presented by cohort. The SMC may also be provided with expected and observed rates of the expected AEs in an unblinded fashion, and may request the treatment assignment be unblinded for an individual subject if required for safety assessment. The SMC will review grouped and unblinded data in the closed session only. The SMC will meet and review this data at scheduled time points or ad hoc as needed during this trial as defined in the SMC charter. As an outcome of each review/meeting, the SMC will make a recommendation as to the advisability of proceeding with study vaccinations (as applicable), and to continue, modify, or terminate this trial.

DMID or the SMC chair may convene the SMC on an ad hoc basis according to protocol criteria or if there are immediate concerns regarding observations during the course of this trial. The DMID Medical Monitor is empowered to stop enrollment and study vaccinations if adverse events that meet the halting criteria are reported. The DMID Medical Monitor and the ISM (as deemed necessary) will be responsible for reviewing SAEs in real time. The SMC will review SAEs on a regular basis and ad hoc during this trial.

10 CLINICAL MONITORING

10.1. Site Monitoring Plan

Site monitoring is conducted to ensure that the human subjects' protections, study and laboratory procedures, study intervention administration, and data collection processes are of high quality and meet sponsor, ICH/GCP guidelines and applicable regulations, and that this trial is conducted in accordance with the protocol, protocol-specific MOP and applicable sponsor standard operating procedures. DMID, the sponsoring agency, or its designee will conduct site-monitoring visits as detailed in the clinical monitoring plan.

Site visits will be made at standard intervals as defined by DMID and may be made more frequently as directed by DMID. Monitoring visits will include, but are not limited to, review of regulatory files, accountability records, eCRFs, informed consent forms, medical and laboratory reports, and protocol and GCP compliance. Site monitors will have access to each participating VTEU site, study personnel, and all study documentation according to the DMID-approved site monitoring plan. Study monitors will meet with site principal investigators to discuss any problems and actions to be taken and document visit findings and discussions.

11 STATISTICAL CONSIDERATIONS

This is a Phase 1, randomized, double-blind trial of 60 males and non-pregnant females, 18-45 years old, inclusive, who are in good health, meet all eligibility criteria, and do not meet any exclusion criteria. This trial is designed to assess the safety, reactogenicity and immunogenicity of a *Zaire ebolavirus* (ChAd3-EBO-Z) vaccine for the prevention of Ebola virus disease. ChAd3-EBO-Z will be administered intramuscularly on Day 1 followed by either placebo (Group 1), ChAd3-EBO-Z (Group 2), or MVA- BN®-Filo (Group 3) at Day 8. The clinical trial includes an exploratory systems biology component to identify changes in gene expression that are associated with adaptive humoral and/or cellular immune responses.

11.1. Study Hypotheses

This Phase I study is not designed to test a formal null hypothesis. The sample size for this study was selected to obtain preliminary estimates of vaccine safety and immunogenicity. The clinical trial includes an exploratory systems biology component to identify changes in gene expression, and cytokines that are associated with adaptive humoral and/or cellular immune responses. These systems biology results are expected to generate hypotheses to be verified in future studies.

11.2. Sample Size Considerations

See [Section 11.1](#) and [Section 4](#).

11.3. Planned Interim Analyses

11.3.1. Interim Safety Review

An interim safety review may include enrollment and demographic information, medical history, concomitant medications, physical assessments, dosing compliance, protocol adherence, clinical laboratory values, and solicited and unsolicited AEs. Additional data may be requested by the SMC, and interim safety reports may be generated as deemed necessary and appropriate by DMID. The SMC will receive data in aggregate. The SMC may request the treatment group be unblinded for an individual subject if required for safety assessment. The SMC will review grouped and unblinded data in the closed session only. The SMC will meet and review this data at scheduled time points or ad hoc as needed during this trial as defined in the SMC charter. As an outcome of each review/meeting, the SMC will make a recommendation as to the advisability of proceeding with study vaccinations (as applicable), and to continue, modify, or terminate this trial.

11.3.2. Interim Immunogenicity Review

An interim immunogenicity review is not planned.

11.4. Final Analysis Plan

The final CSR will be completed after the last subject's last visit is completed, and the final clinical database including all long-term safety follow-up data is cleaned, monitored and locked. The primary CSR will include results for all primary and secondary endpoint data as well as exploratory EBOV GP pseudovirion neutralization assay data. Additional results for exploratory endpoint data will be included as one or more addenda to the primary CSR. A formal Statistical Analysis Plan that specifies all planned analyses will be developed and finalized prior to the final clinical database lock.

11.4.1. Analysis Populations

The Safety Analysis population includes all subjects who received at least one study vaccination.

The intent-to-treat (ITT) population includes all subjects who received at least one study vaccination and contributed both pre- and at least one post-study vaccination blood samples for immunogenicity testing for which valid results were reported. Subjects will be analyzed according to the study group to which they were randomized.

The per protocol (PP) population includes all subjects in the ITT subset with the following exclusions:

- Data from all available visits for subjects found to be ineligible at baseline.
- Data from all visits subsequent to major protocol deviations, such as:
 - Second study vaccination not received,
 - Receipt of non-study licensed live vaccine within 30 days prior to or after each study vaccination,
 - Receipt of non-study licensed inactivated vaccine within 14 days prior to or after each study vaccination,
 - Receipt of oral or parenteral (including intraarticular) corticosteroids of any dose within 30 days prior to study vaccination.
 - Receipt of high-dose inhaled corticosteroids within 30 days prior to study vaccination.
 - Receipt of chronic (defined as more than 14 days) immunosuppressants or other immune modifying drugs within 6 months of receipt of study vaccine.
- Data from any visit that occurs outside the pre-defined protocol window.
- In the case of mis-randomization, subjects will be analyzed according to the study product actually received.

11.4.2. Safety Data

Safety data will be summarized for the Safety Analysis Population. Pre-second vaccination, Study Groups 1, 2, 3 will be analyzed jointly as one study group as all three groups received the same vaccine at Day 1.

Solicited AEs will be summarized by severity for each day after each study vaccination (Days 1 through 7 days post-vaccination) and as the maximum severity over all days after each vaccination. The maximum severity of local and systemic reactions will be determined for each subject and summarized by study group following each vaccination (as well as post any vaccination) and the resulting number, percentage (observed rate) of subjects and associated exact 95% confidence interval (CI) will be summarized by severity grade (none, mild, moderate, severe) and symptom. Summaries will also be provided for any systemic symptoms, for any local symptoms, and for any systematic or local symptoms.

Vaccine-related unsolicited AEs from the first study vaccination through 28 days post second vaccination will be coded by Medical Dictionary for Regulatory Activities (MedDRA®) for preferred term and system organ class (SOC). These AEs will be summarized as number and percentage of subjects reporting at least one event in each MedDRA® preferred term and SOC, cross tabulated by severity grade (none, mild, moderate, severe). Additionally, the number, percentage (observed rate) and exact two-sided 95% CI for subjects reporting a related unsolicited AE overall, by SOC, and by preferred term will be summarized by study group.

Clinical safety laboratory AEs from the time of first study vaccination through approximately 28 days after the second vaccination will be summarized by severity grade (none, mild, moderate, severe) for each laboratory visit. In addition, the maximum severity over all post-vaccination visits will be summarized by study visit and by severity grade (none, mild, moderate, severe) using percentages and exact two-sided 95% CIs.

The number of SAEs and vaccine-related Medically Attended Adverse Events (MAAEs) through 6 months post first vaccination will be reported by detailed listings showing the event description, preferred term and SOC, relevant dates (study vaccinations and AEs), severity, vaccine-relatedness, and outcome for each event.

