3.2. Study Outcome Measures

3.2.1. Primary

- Frequency and severity of solicited local and systemic reactogenicity from the time of study vaccine administration through 7 days post-vaccination.
- Frequency and severity of vaccine-related unsolicited adverse events (AEs) from the first study vaccination through 28 days post second vaccination.

- Frequency and severity of clinical safety laboratory AEs from the time of first study vaccination through approximately 28 days after the second vaccination.
- Frequency of Serious Adverse Events (SAEs) and vaccine-related Medically Attended Adverse Events (MAAEs) through 6 months post first vaccination.

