14.3 Safety Data

14.3.1 Displays of Adverse Events

Table 23: Overall Summary of Adverse Events

	Study Arm 1 ChAd3+Placebo (N=X)		Study Arm 2 ChAd3+ChAd3 (N=X)		Study Arm 3 ChAd3+MVA-BN (N=X)		All Subjects (N = X)	
Subjects* with	n	n%	n	%	n	%	n	%
At least one local solicited adverse event	x	x.x	x	x.x	x	x.x	x	x.x
At least one systemic solicited adverse event	x	x.x	x	x.x	x	x.x	x	x.x
At least one laboratory adverse event	x	x.x	x	x.x	x	x.x	x	x.x
At least one vaccine-related unsolicited adverse event	x	x.x	x	x.x	x	x.x	x	x.x
Mild (Grade 1)	x	x.x	x	x.x	x	x.x	x	x.x
Moderate (Grade 2)	x	x.x	x	x.x	x	x.x	x	x.x
Severe (Grade 3)	x	x.x	x	x.x	x	x.x	x	x.x
At least one serious adverse event [†]	x	x.x	x	x.x	x	x.x	x	x.x
At least one vaccine-related medically attended adverse event [§]	x	x.x	x	x.x	x	x.x	x	x.x

N = Number of subjects in the Safety Population. *: Subjects are counted once for each category regardless of the number of events. [†]: A listing of Serious Adverse Events is included in Table 28. [‡]: As reported on the Adverse Event eCRF. [§]: All vaccine-related medically attended adverse events are included in Table 29.

14.3.1.1 Solicited Adverse Events**Table 24: Number and Percentage of Subjects Experiencing Solicited Events with 95% Confidence Intervals by Symptom, Dose, and Treatment Group**

Symptom	Post Dose 1 Study Arm 1,2,3 ChAd3 (N=X)*			Post Dose 2 Study Arm 1 ChAd3+Placebo (N=X)			Post Dose 2 Study Arm 2 ChAd3+ChAd3 (N=X)			Post Dose 2 Study Arm 3 ChAd3+MVA-BN (N=X)			Post Either Dose Study Arm 1 ChAd3+Placebo (N=X)			Post Either Dose Study Arm 2 ChAd3+ChAd3 (N=X)			Post Either Dose Study Arm 3 ChAd3+MVA-BN (N=X)		
	n	%	95% CI†	n	%	95% CI†	n	%	95% CI†	n	%	95% CI†	n	%	95% CI†	n	%	95% CI†	n	%	95% CI†
Any Symptom	x	x.x	x.x, x.x	x	x.x	x.x, x.x	x	x.x	x.x, x.x	x	x.x	x.x, x.x	x	x.x	x.x, x.x	x	x.x	x.x, x.x	x	x.x	x.x, x.x
Any Systemic Symptom	x	x.x	x.x, x.x	x	x.x	x.x, x.x	x	x.x	x.x, x.x	x	x.x	x.x, x.x	x	x.x	x.x, x.x	x	x.x	x.x, x.x	x	x.x	x.x, x.x
Elevated Oral Temperature	x	x.x	x.x, x.x	x	x.x	x.x, x.x	x	x.x	x.x, x.x	x	x.x	x.x, x.x	x	x.x	x.x, x.x	x	x.x	x.x, x.x	x	x.x	x.x, x.x
Feverishness	x	x.x	x.x, x.x	x	x.x	x.x, x.x	x	x.x	x.x, x.x	x	x.x	x.x, x.x	x	x.x	x.x, x.x	x	x.x	x.x, x.x	x	x.x	x.x, x.x
Malaise	x	x.x	x.x, x.x	x	x.x	x.x, x.x	x	x.x	x.x, x.x	x	x.x	x.x, x.x	x	x.x	x.x, x.x	x	x.x	x.x, x.x	x	x.x	x.x, x.x
Fatigue	x	x.x	x.x, x.x	x	x.x	x.x, x.x	x	x.x	x.x, x.x	x	x.x	x.x, x.x	x	x.x	x.x, x.x	x	x.x	x.x, x.x	x	x.x	x.x, x.x

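### SAEs and vaccine-related MAAEs through 6 months are the only one of the four primary outcomes with no planned confidence interval

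*Protocol*

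**What the plan says.** Protocol 3.2.1 and SAP 3.2.1 list the same four primary outcomes. The fourth is: "Frequency of Serious Adverse Events (SAEs) and vaccine-related Medically Attended Adverse Events (MAAEs) through 6 months post first vaccination".

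Protocol 11.4.2 plans an exact interval for each of the first three:

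- Solicited events: "percentage (observed rate) of subjects and associated exact 95% confidence interval (CI) will be summarized by severity grade". The SAP displays are Tables 24 and 25.
- Vaccine-related unsolicited AEs: "percentage (observed rate) and exact two-sided 95% CI for subjects reporting a related unsolicited AE overall, by SOC, and by preferred term". The SAP display is Table 27.
- Laboratory AEs, by severity grade: "using percentages and exact two-sided 95% CIs". The SAP display is Table 35.

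For the fourth outcome the same section says: "The number of SAEs and vaccine-related Medically Attended Adverse Events (MAAEs) through 6 months post first vaccination will be reported by detailed listings". SAP 9.4 repeats the sentence and points to the listings in Tables 30 and 31. The only planned proportion is in SAP Table 23, in the rows "At least one serious adverse event" and "At least one vaccine-related medically attended adverse event". These show n and % for each arm and for all subjects, with no interval.

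On the purpose of the sample, Protocol 11.1 says: "The sample size for this study was selected to obtain preliminary estimates of vaccine safety and immunogenicity". SAP Section 5 says the same, and both state that no formal null hypothesis is tested.

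**The concern.** With no hypothesis test, the interval estimates carry the trial's inference. They are planned for three primary outcomes and left out for the fourth, without a stated reason. The fourth is also the outcome where a bare percentage says least. SAEs are rare in healthy adults, so the expected display is 0 (0.0%) in Table 23 and an empty Table 30.

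At stake is how a clean result would be read. A 0.0% in an arm of 20 is compatible with a risk well above zero, and as planned the report would not say how far above.

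**Working it through.** **Is there an interval elsewhere?** SAP 6.1 sets frequency and percentage as the default for categorical data, with no interval. SAP Table 28 gives intervals for any unsolicited AE by system organ class and preferred term, but does not isolate SAEs. SAP Table 27 covers vaccine-related unsolicited AEs. SAP 9.3.2 limits those to 28 days after the second vaccination, and the table does not isolate MAAEs. The other primary outcomes also have displays without intervals (Tables 26 and 29), but each has at least one table with them. So the statement holds at the level of the outcome.

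**Inputs**

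- Subjects: 20 per arm and 60 in total (Protocol Section 4, Table 1; SAP Table 1).
- Method: exact Clopper-Pearson 95% interval (SAP 9.3.1).
- Adult SAE rates over one year in the phase 2 studies: 11 subjects (0.7%) in the EBO-Z group and 18 (1.2%) in the Placebo/EBO-Z group (Protocol 2.3.1, Safety in Phase II Studies).
- Rate of vaccine-related MAAEs: none given.

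The documents state no precision target to reproduce: Protocol 11.2 only refers back to 11.1 and Section 4.

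**Upper limits.** For a zero count the two-sided 95% upper limit is 1 − 0.025^(1/n):

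- 0/20: 1 − 0.025^(1/20) = 16.8%
- 0/60: 1 − 0.025^(1/60) = 6.0%

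For one event the interval comes from beta quantiles:

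- 1/20 = 5.0%, interval 0.1% to 24.9%
- 1/60 = 1.7%, interval 0.04% to 8.9%

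**Chance of zero SAEs.** P(0) = (1 − p)^n. The 6-month risk under a constant hazard is p6 = 1 − (1 − p12)^0.5. This gives 0.351% from 0.7% and 0.602% from 1.2%.

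| Risk used | P(0 in 20) | P(0 in 60) |
|---|---|---|
| 0.351% (0.7% scaled to 6 months) | 93% | 81% |
| 0.602% (1.2% scaled to 6 months) | 89% | 70% |
| 0.7% unscaled | 87% | 66% |
| 1.2% unscaled | 79% | 48% |

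Zero is the most likely single count whenever p < 1/(n + 1), that is below 1/61 = 1.6% for 60 subjects and 1/21 = 4.8% for 20. All four risks are below both thresholds. At 1.2% unscaled, at least one SAE in 60 (52%) is slightly more likely than none, but no other single count is as likely as zero.

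**The case against.** The outcome as worded asks for a frequency, and Table 23 delivers one by arm and overall, with every event listed in Tables 30 and 31. An exact binomial interval depends only on n and N, and both are in Table 23. A reader might infer that nobody could tell what rate the trial had excluded. The documents do not support that: the bound can be derived, and what is missing is the report stating it.

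No decision turns on the interval. The plan sets no SAE-rate criterion, and the halting rules in Protocol 9.5 act on a single product-related SAE. For rare events in arms of 20, case listings are a sensible main display. This stands, and it limits the weight of the point.

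The MAAE half is weaker. A reader might extend the zero-count argument to vaccine-related MAAEs, but the documents give no rate for them. Protocol 9.2.1 also defines MAAEs among unsolicited AEs, so vaccine-related ones up to 28 days after the second vaccination fall within the overall interval in Table 27. That interval neither isolates them nor extends to 6 months.

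A reader might also take 6.0% as a bound for each regimen. It is not, because a pooled interval through 6 months mixes three different regimens. The plan pools arms for its interval estimates only before the second vaccination, when all have received the same product. Denominators may also differ from 20 and 60: Protocol 5.4.1 and 5.4.5 allow replacement of vaccinated subjects who leave, while the Safety population keeps everyone vaccinated at least once. Some of these may lack 6 months of follow-up.

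None of this explains why three primary outcomes get an interval and the fourth does not.

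**Conclusion.** The gap is real and its consequence is modest. The fourth primary outcome is the only one without a planned interval, in a trial sized to give estimates. For SAEs a zero count is the most likely result. The likely display is therefore 0.0% with no stated bound, where the plan's own method gives an upper limit of 16.8% for 0/20 and 6.0% for 0/60.

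The probabilities assume that the phase 2 adult rates carry over to this population and to two vaccinations a week apart. The 70% to 81% range also assumes a constant hazard over the year. Quoting 81% alone would use only the lower of the two rates. Zero remains the most likely SAE count across the whole range of 48% to 81%. The limits assume exactly 20 and 60 subjects with complete follow-up. Nothing is claimed about the likely number of vaccine-related MAAEs.

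**What to change.** In Protocol 11.4.2, SAP 9.4 and SAP Table 23:

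- Report the number and percentage of Safety-population subjects with at least one SAE, and with at least one vaccine-related MAAE, through 6 months. Give exact Clopper-Pearson 95% intervals by arm on the actual denominators.
- If an all-subjects interval is shown, label it as a descriptive pool of three regimens.
- State for each arm how many subjects completed the 6-month follow-up.
- Keep the listings in Tables 30 and 31.

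The cost is interval entries for two rows of Table 23, one sentence in each of the two sections, and a follow-up count that SAP Table 14 already plans. No other row of Table 23 has an interval, so a short companion table would serve equally well if a uniform overview is preferred. Table 23 needs an edit in any case: its footnotes send the reader to Tables 28 and 29 for the SAE and MAAE listings, which are Tables 30 and 31. No new data, visits or subjects are needed.
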